6.6 Additional treatment guidance

Tumor Lysis Syndrome (TLS) TLS was observed in subjects diagnosed with hematological malignancies (AML) and administered siremadlin in study CHDM201X2101 with siremadlin. One subject, who had grade 4 TLS, was treated according to regimen 2C (daily dosing Day 1-7, Q4W) at 45 mg siremadlin dose. During this study, including the extension treatment phase, subjects receiving siremadlin should be closely monitored (including relevant laboratory tests) for signs and symptoms of TLS before initiation and during a treatment cycle. Risk assessment of TLS, prophylaxis and events should be managed according to the institutional guidelines.

Before initiation of a treatment cycle and during a treatment cycle, the following measures should be followed:

- Prophylaxis (i.e. allopurinol) for TLS should be administered.
- Oral fluids are recommended
- Prompt supportive care in case of acute TLS (IV fluids and rasburicase as clinically indicated, when uric acid continues to rise despite allopurinol/febuxostat and fluids)

During a treatment cycle:

- Frequent monitoring of the following laboratory tests (per Table 8-2 and Table 8-3 and as clinically indicated): potassium, phosphorus, calcium, creatinine, and uric acid
- Encourage oral hydration

Based on laboratory and clinical TLS criteria (modified from Cairo and Bishop 2004), the following measures for TLS should be also followed

Laboratory tumor lysis syndrome

Defined as two or more of the following values within three days before or in the days following initiation of a treatment cycle:

- Uric acid ≥ 8 mg/dL or 25% increase from baseline
- Potassium \geq 6 mEq/L or 25% increase from baseline
- Phosphorus or $\geq 4.5 \text{ mg/dL}$ or 25% increase from baseline
- Calcium \leq 7 mg/dL or 25% decrease from baseline

Regimen:

- If none or one of the laboratory values above is abnormal, continue to manage with allopurinol or a non-allopurinol alternative (e.g. febuxostat) and oral fluids. If uric acid remains elevated, consider IV fluids, rasburicase, and hospital monitoring.
- Laboratory TLS should be managed with IV fluids, laboratory blood tests every 6 to 8 hours and inpatient care. Cardiac monitoring and rasburicase should be considered if uric acid remain elevated.

Clinical tumor lysis syndrome

Defined as the presence of laboratory TLS and ≥ 1 of the following criteria that cannot be explained by other causes:

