8.4 Safety and tolerability

Safety assessments are specified below in Table 8-9 and Table 8-10 and with the assessment schedule in Table 8-2, Table 8-3, Table 8-4 and Table 8-5 detailing when each assessment is to be performed during the study. These include a physical examination, vital signs, weight, laboratory assessments, ECOG performance status and ECGs, as well as the collection of AEs at every clinic visit. For details on AE collection and reporting, refer to Section 10.1

As per Section 4.6, during a Public Health emergency as declared by Local or Regional authorities i.e. pandemic, epidemic or natural disaster, that limits or prevents on-site study visits, regular phone or virtual calls can occur (every 4 weeks or more frequently if needed) for safety monitoring and discussion of the subject's health status until it is safe for the subject to visit the site again.

Additional safety monitoring for Tumor Lysis Syndrome (TLS)

TLS is a known risk for patients with hematological malignancies, and was observed in two subjects diagnosed with AML and administered siremadlin in study CHDM201X2101. Therefore, additional safety assessments will be collected for subjects on the ruxolitinib and Amended Protocol Version No 09 (Clean)

siremadlin arm in this study to monitor for signs and symptoms of TLS. In addition to the full chemistry panel collected as outlined in Table 8-2 and Table 8-3, phosphorus, calcium, uric acid, potassium, and creatinine will also be measured on Days 2, 5 and 6 of Cycle 1 and Cycle 2, and Days 2 and 5 for Cycles 3-6, and then only when clinically indicated. Refer to Section 6.6 for additional information.

Table 8-9 Safety & tolerability assessments & specifications

Assessment	Specification
Physical	A complete physical examination will include the examination of general appearance, skin, neck (including thyroid), eyes, ears, nose, throat, lungs, heart, abdomen, back, lymph nodes, extremities, vascular, and neurological. A complete physical examination should be conducted at screening and baseline (pre-dose C1D1) for Parts 1, 2 and 3 of the study. If indicated, based on medical history and/or symptoms, rectal, external genitalia, breast, and pelvic examinations will be performed.

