In addition, all AEs and SAEs which started during the overall safety period will be summarized.

A subject with multiple adverse events within a primary system organ class is only counted once towards the total of the primary system organ class.

All AEs, deaths and serious adverse events (including those from the pre, on-extension treatment period and post-treatment periods) will be listed and those started during the pre-treatment period, post-treatment period, and post-treatment/overall safety overlapping period will be flagged.

Vital signs

All vital signs data will be listed by treatment group, subject, and visit/time and if ranges are available, abnormalities (and relevant orthostatic changes) will be flagged. Summary statistics will be provided by treatment group for core treatment phase.

12-lead ECG

All ECG data will be listed by treatment group, subject and visit/time, abnormalities will be flagged. Summary statistics will be provided by treatment group for core treatment phase.

Clinical laboratory evaluations

All laboratory data will be listed by treatment group, subject, and visit/time and if normal ranges are available abnormalities will be flagged. Summary statistics will be provided by treatment and visit/time for core treatment phase. Shift tables using the low/normal/high/ (low and high) classification will be used to compare baseline to the worst on-treatment value for core treatment phase.

Grading of laboratory values will be assigned programmatically as per NCI Common Terminology Criteria for Adverse Events (CTCAE) version 5.0. The calculation of CTCAE grades will be based on the observed laboratory values only, clinical assessments will not be taken into account.

CTCAE Grade 0 will be assigned for all non-missing values not graded as 1 or higher. Grade 5 will not be used.

For laboratory tests where grades are not defined by CTCAE v5.0, results will be categorized as low/normal/high based on laboratory normal ranges.

The following summaries will be generated separately for hematology, and biochemistry tests:

5. Listing of all laboratory data with values flagged to show the corresponding CTCAE v5.0 grades if applicable and the classifications relative to the laboratory normal ranges

For laboratory tests where grades are defined by CTCAE v5.0:

- Worst post-baseline CTCAE grade (regardless of the baseline status). Each subject will be counted only once for the worst grade observed post-baseline.

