Safety summaries (tables, figures) include data from the pre-treatment period (to display the baseline status e.g. for ECG) and the on-treatment period, i.e. data from the post-treatment period with the exception of deaths should not be included unless requested from Health Authorities or external committees.

In particular, summary tables for adverse events (AEs) will summarize on-treatment events, with a start date during the on-treatment period, the so-called ***treatment-emergent*** AEs. Additionally, all (study treatment related/ regardless) AEs and SAEs with a start date during the overall safety period will be summarized.

However, all safety data (including those from the post-treatment period) will be listed and those collected during the pre-treatment, post-treatment overall safety period and post-treatment period are to be flagged.

For the final analysis, all extension treatment phase safety data will be listed and those collected during post-treatment overall safety period and post-treatment period are to be flagged. The safety data in part 1 core and extension phase will be summarized in tables for the extension treatment phase clinical trial safety disclosure.

Windows for multiple assessments

In order to summarize data collected over time (including unscheduled visits), the assessments will be time slotted. The following general rule will be applied in creating the assessment windows: If more than one assessment is done within the same time window, the assessment performed closest to the target date will be used. If two assessments within a time window are equidistant from the target date, then the assessment that occurred later will be used. If multiple assessments occur on the same date then the worst case will be used. Data from all assessments (scheduled and unscheduled), including multiple assessments, will be listed.

The following time windows are defined for descriptive summary on spleen imaging, spleen length palpation, ePROs, laboratory assessments [REDACTED] (Tables 2-1, 2-2, and 2-3) by visit regardless of core or extension treatment phases. The end of treatment assessment will be mapped into the time points as needed.

Table 2-1 Time windows for imaging assessments (MRI/CT of abdomen)

Time Point	Planned Visit Timing	Time Window Definition
Screening/Baseline	On or before Study Day 1*	≤ Study Day 1
Cycle 7 Day 1	Study Day 168	Study Days 140 – 196
Cycle 13 Day 1	Study Day 336	Study Days 308 – 364
Every 6 cycles thereafter		

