Cycle $y=13+6*k$ Day 1 (with $k = 1, 2, \dots$)	Study Day $(13+6*k-1)*28$	Study Days $(13+6*k-1)*28-28$ to $(13+6*k-1)*28+28$

* Study Day 1 = Date of first administration of study treatment (start of study treatment)

EOT core and EOT extension assessments are mapped to the corresponding time points based on the defined time window.

Table 2-2 Time windows for ePROs, laboratory assessments (chemistry, coagulation, urinalysis and thyroid function) [REDACTED]

Time Point	Planned Visit Timing	Time Window Definition
Baseline (Cycle 1 Day 1)	On or before Study Day 1*	≤ Study Day 1
Cycle 2 Day 1	Study Day 29	Study Days 15 – 42
Cycle 3 Day 1	Study Day 57	Study Days 43 – 70
Cycle 4 Day 1	Study Day 85	Study Days 71 – 98

Cycle 5 Day 1	Study Day 113	Study Days 99 – 126
Cycle 6 Day 1	Study Day 141	Study Days 127 – 154
Cycle 6+k Day 1 (with k = 1, 2, ...)	Study Day (6+k-1)*28+1	Study Day (6+k-1)*28+1-14 to (6+k-1)*28+14
Post treatment		
30-day safety follow-up	Post treatment study day 30	Post treatment study days 23 – 37
90-day safety follow-up	Post treatment study day 90	Post treatment study days 83 – 97
105-day safety follow-up	Post treatment study day 105	Post treatment study days 98 – 112
150-day safety follow-up	Post treatment study day 150	Post treatment study days 136 – 164

* Study Day 1 = Date of first administration of study treatment (start of study treatment)
 EOT core and EOT extension assessments are mapped to the corresponding time points based on the defined time window.
 Post treatment study day 1 = end of study treatment date + 1
 Post treatment visits are for laboratory chemistry assessments only
 90-day safety follow-up visit for NIS7393 arm(s)
 90-day safety follow-up visit, and 150-day safety follow up visit are for sabatolimab arm(s)
 105-day safety follow-up visit is for crizanlizumab arm(s)

Table 2-3 Time windows for spleen length palpation assessments and hematology laboratory assessments

Time Point	Planned Visit Timing	Time Window Definition
Baseline (Cycle 1 Day 1)	On or before Study Day 1*	≤ Study Day 1
Cycle 1 Day 15	Study Day 15	Study Days 8 – 21
Cycle 2 Day 1	Study Day 29	Study Days 22 – 35
Cycle 2 Day 15	Study Day 43	Study Days 36 – 49
Cycle 3 Day 1	Study Day 57	Study Days 50 – 63
Cycle 3 Day 15	Study Day 71	Study Days 64 – 77
Cycle 4 Day 1	Study Day 85	Study Days 78 – 98
Cycle 5 Day 1	Study Day 113	Study Days 99 – 126
Cycle 6 Day 1	Study Day 141	Study Days 127 – 154

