2.8.3 Laboratory data

Data from all sources (central and local laboratories) will be combined. The summaries will include all laboratory assessments collected no later than 30 days after the last study treatment administration date. Laboratory data will be listed by treatment group, subject, and visit/time and if normal ranges are available abnormalities will be flagged. Summary statistics will be provided by treatment and visit/time. Shift tables using the low/normal/high/ (low and high) classification will be used to compare baseline to the worst on-treatment value.

Grading of laboratory values will be assigned programmatically as per NCI Common Terminology Criteria for Adverse Events (CTCAE) version 5.0. The calculation of CTCAE grades will be based on the observed laboratory values only, clinical assessments will not be taken into account.

CTCAE Grade 0 will be assigned for all non-missing values not graded as 1 or higher. Grade 5 will not be used.

For laboratory tests where grades are not defined by CTCAE v5.0, results will be categorized as low/normal/high based on laboratory normal ranges.

The following summaries will be generated separately for hematology, and biochemistry tests:

- Listing of all laboratory data with values flagged to show the corresponding CTCAE v5.0 grades if applicable and the classifications relative to the laboratory normal ranges. Lab data collected during the post-treatment period will be flagged.
- Listing of all CTCAE grade 3 or 4 laboratory toxicities

For laboratory tests where grades are defined by CTCAE v5.0:

- Worst post-baseline CTCAE grade (regardless of the baseline status). Each subject will be counted only once for the worst grade observed post-baseline.
- Shift tables using CTCAE v5.0 grades to compare baseline to the worst on-treatment value

For laboratory tests where grades are not defined by CTCAE v5.0:

- Shift tables using the low/normal/high/ (low and high) classification to compare baseline to the worst on-treatment value.

Liver function parameters

Liver function parameters of interest are total bilirubin (TBIL), ALT, AST and alkaline phosphatase (ALP). The number (%) of patients with worst post-baseline values as per Novartis Liver Toxicity guidelines will be summarized:

The following summaries will be produced:

- ALT or AST > 3xULN
- ALT or AST > 5xULN
- ALT or AST > 10xULN
- ALT or AST > 20xULN
- ALP > 1.5xULN
- TBL > 2xULN
- ALT or AST > 3xULN & TBL > 2xULN

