		5(11.1%)	0.6408	0.3327	0.1349	0.0443	0.0120
		7(15.6%)	0.8247	0.5586	0.3004	0.1301	0.0461
		9(20.0%)	0.9247	0.7456	0.4971	0.2709	0.1210

Number of responders in combination treatment arm n _{combo} = 45	11(24.4%)	0.9710	0.8706	0.6794	0.4462	0.2433
	13(28.9%)	0.9899	0.9415	0.8184	0.6219	0.4015
	15(33.3%)	0.9968	0.9763	0.9083	0.7688	0.5701
	17(37.8%)	0.9991	0.9914	0.9587	0.8737	0.7217
	19(42.2%)	0.9998	0.9972	0.9835	0.9386	0.8387
	21(46.7%)	0.9999	0.9992	0.9941	0.9735	0.9167
	23(51.1%)	1.0000	0.9998	0.9981	0.9899	0.9620
	25(55.6%)	1.0000	1.0000	0.9995	0.9966	0.9848
	27(60.0%)	1.0000	1.0000	0.9999	0.9990	0.9947
	Number of responders in ruxolitinib monotherapy arm n _{rux} = 40					
Number of responders in combination treatment arm n _{combo} = 45	3 (7.5%)	5 (12.5%)	7 (17.5%)	9 (22.5%)	11 (27.5%)	
	5(11.1%)	0.7124	0.4200	0.1994	0.0786	0.0263
	7(15.6%)	0.8756	0.6546	0.4036	0.2068	0.0892
	9(20.0%)	0.9531	0.8235	0.6141	0.3884	0.2079
	11(24.4%)	0.9842	0.9213	0.7822	0.5823	0.3735
	13(28.9%)	0.9952	0.9691	0.8922	0.7482	0.5555
	15(33.3%)	0.9987	0.9892	0.9530	0.8661	0.7192
	17(37.8%)	0.9997	0.9966	0.9819	0.9372	0.8428
	19(42.2%)	0.9999	0.9991	0.9938	0.9740	0.9223
	21(46.7%)	1.0000	0.9998	0.9981	0.9906	0.9662
	23(51.1%)	1.0000	1.0000	0.9995	0.9970	0.9872
	25(55.6%)	1.0000	1.0000	0.9999	0.9992	0.9958
	27(60.0%)	1.0000	1.0000	1.0000	0.9998	0.9988

4 Change to protocol specified analyses

No change from protocol specified analysis was made according to protocol amendment 8 per Protocol section 12.

5 Appendix

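### With visits on schedule, the SAP's chemistry windows leave all 14 scheduled siremadlin tumour lysis draws out of the by-visit laboratory summaries

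*SAP*

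**What the plan says.** Protocol 8.4 adds TLS monitoring for subjects on ruxolitinib plus siremadlin: "phosphorus, calcium, uric acid, potassium, and creatinine will also be measured on Days 2, 5 and 6 of Cycle 1 and Cycle 2", then on Days 2 and 5 of Cycles 3-6. Table 8-2 carries these draws as database-recorded assessments. Protocol 6.6 sets the time frame that matters for laboratory TLS: "Defined as two or more of the following values within three days before or in the days following initiation of a treatment cycle". The listed criteria are absolute limits or 25% changes from baseline.

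For reporting, SAP 2.8.3 plans: "Summary statistics will be provided by treatment and visit/time". Protocol 12.5.2 has the same commitment for the core phase.

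SAP 2.1.1 says how over-time summaries are built: "In order to summarize data collected over time (including unscheduled visits), the assessments will be time slotted". Within a slot, "If more than one assessment is done within the same time window, the assessment performed closest to the target date will be used". Chemistry is assigned to Table 2-2. Its baseline slot ends on Study Day 1 and its first post-baseline slot, Cycle 2 Day 1, covers "Study Days 15 – 42". Each later slot is centred on Day 1 of a cycle. By contrast, Table 2-3 gives hematology its own Day 15 slots in Cycles 1-3.

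**The concern.** The extra draws exist because TLS, including a Grade 4 case, was seen with siremadlin in an earlier study. They sample the dosing days and the day after. By-visit tables are where a reader sees the average size and timing of a change, and these tables are blind on exactly those days. A shift present on Day 2 in every subject and gone by Day 29 would leave every by-visit mean unchanged, whatever its size.

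The other planned tables replace this only in part. Shift tables use CTCAE grade or low/normal/high categories and take one worst value per subject over the whole on-treatment period. They therefore lose the timing, and a 25% change that stays within the normal range may not register. SAP 2.8.3 adds specific summaries for liver function but none for TLS chemistry.

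A second problem appears when visits move. The rule can then put a value from a dosing day, or the day after, into a row labelled Day 1, with nothing in the table to show it.

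**Working it through.** **Inputs.** Draw days: Protocol 8.4 and Table 8-2. Dosing on Days 1-5 of a 28-day cycle: Protocol 6.7.2.2. Windows and selection rule (a tie goes to the later sample): SAP 2.1.1 and Table 2-2.

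**The plan's own figures.** Target day for cycle c is 28(c-1)+1, which gives 29, 57, 85, 113 and 141 for Cycles 2-6. These match Table 2-2.

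**Number of draws.** 2 cycles x 3 + 4 cycles x 2 = 14.

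**Slotting, visits on schedule.** Day d of cycle c is Study Day 28(c-1)+d.

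| Cycle | TLS draws (Study Day) | Slot | Target | Days from target: TLS draws | Days from target: Day 1 sample |
|---|---|---|---|---|---|
| 1 | 2, 5, 6 | none | – | – | – |
| 2 | 30, 33, 34 | 15-42 | 29 | 1, 4, 5 | 0 |
| 3 | 58, 61 | 43-70 | 57 | 1, 4 | 0 |
| 4 | 86, 89 | 71-98 | 85 | 1, 4 | 0 |
| 5 | 114, 117 | 99-126 | 113 | 1, 4 | 0 |
| 6 | 142, 145 | 127-154 | 141 | 1, 4 | 0 |

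Three draws have no slot and 11 lose to the Day 1 sample, so 0 of 14 are used.

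**Share.** Through Cycle 6 there are 5 post-baseline Day 1 panels, so 14/(14+5) = 14/19 = 74% of scheduled post-baseline time points for the five analytes are not summarised by visit. Counting the EOT and 30-day follow-up panels as well gives 14/21 = 67%.

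**Time since last dose.** The Day 1 sample of cycle c follows the Day 5 dose of cycle c-1 by [28(c-1)+1] - [28(c-2)+5] = 24 days. This assumes the sample is drawn before that day's dose, which the schedule does not state for chemistry.

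**Visits off schedule.**
- Early Day 1. One day early: the Day 2 draw hits the target and is used. Two days early: Day 2 is 1 day away and Day 1 is 2. Three days early: the Day 5 draw is 1 day away, Day 2 is 2 and Day 1 is 3. In each case a TLS draw is used.
- Late by 0-3 days, independently in each of Cycles 2-6: 4^5 = 1,024 patterns, and none selects a TLS draw.
- The same delays accumulating from cycle to cycle, with a Cycle 7 Day 1 sample at the accumulated delay: 21 of 1,024 patterns select one or two TLS draws.
- A sustained 12-day delay: Cycle 2 Day 6 falls on 34+12 = 46, 11 days from target 57. Cycle 3 Day 1 falls on 57+12 = 69, 12 days away. The Cycle 2 Day 6 draw is used as Cycle 3 Day 1. At 11 days the distances are 12 and 11 and the Day 1 sample is kept. At 13 days, five rows are filled by TLS draws.
- A missing Cycle 2 Day 1 sample: the Cycle 2 Day 2 draw (Study Day 30) fills that row.

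**The case against.** **These draws may be a separate item.** Table 8-2 lists the additional chemistry on its own row, and the SAP never says what happens to an assessment outside every slot. Some text near the windows is also redacted. This has some force for the 3 Cycle 1 draws. But SAP 2.1.1 slots all data summarised over time, even unscheduled visits, and Table 2-2 covers chemistry without exception. All five analytes also belong to the Day 1 panel. Exclusion is what the visible rules produce.

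**By-visit means are a poor tool for TLS.** Laboratory TLS needs two or more abnormal values in one subject, which single-analyte means cannot show. With about 6 subjects per dose cohort, each added row would be thin. This is true and limits the gain. The rows would still show size and timing of change, as by-visit summaries are meant to do.

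**Stronger readings that a reader might infer.**
- *The TLS data are lost to the analysis.* They are not. The windows govern by-visit summaries only. Worst post-baseline grades, shifts to the worst on-treatment value, the grade 3/4 listing and full listings with study day all carry these values.
- *No TLS draw can ever enter a by-visit row.* Early, long-delayed or missing Day 1 samples let one in, as shown above. Table 8-1 allows visits 3 days either side, although Protocol section 8 says siremadlin cycles should not be shortened below 28 days.
- *The tables contain nothing but Day 1 samples 24 days after dosing.* The baseline row precedes any siremadlin, follow-up rows exist, and EOT and unscheduled samples can be slotted.
- *The SAP departs from Protocol 12.5.2, so the statement in SAP section 4 is wrong.* The protocol says "Summary statistics will be provided by treatment and visit/time for core treatment phase" but does not promise a row for every draw. Choosing display time points is ordinary SAP work.

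**Conclusion.** The point holds as a limited defect in the over-time display of siremadlin chemistry. With visits on schedule, 0 of 14 scheduled TLS draws enter a by-visit row: 74% of post-baseline time points through Cycle 6, or 67% with EOT and 30-day follow-up counted. In Cycle 1 nothing between baseline and Study Day 29 is shown from scheduled samples. When Day 1 visits are early, when delays reach about 12 days, or when a Day 1 sample is missing, the opposite fault can occur: a TLS draw reported as a Day 1 value.

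The slotting result rests on the visible SAP text, 28-day cycles and Day 1 samples being taken. The 24-day figure also needs pre-dose sampling. No endpoint estimate, dose decision or subject protection changes. It is still worth correcting, because safety characterisation is the purpose of Part 1 and the data are already collected.

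**What to change.** Add to SAP 2.1.1, next to Table 2-2:

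> For the siremadlin arm, the additional chemistry draws (phosphorus, calcium, uric acid, potassium, creatinine) are summarised by nominal visit in separate rows: C1D2, C1D5, C1D6, C2D2, C2D5, C2D6, and Days 2 and 5 of Cycles 3-6. They are not eligible for the Day 1 windows in Table 2-2.

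The first sentence restores the missing days. The second stops a TLS draw from appearing under a Day 1 label. If the tables are already final, one supplementary table would do the same job.

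The cost is one or two sentences and up to 14 extra rows for five analytes in one arm. No new samples, visits or data collection are needed. The small downside is that each row rests on only about 6 subjects per dose cohort, so it should be read as description.

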30-, 90-, and 105-day Safety Follow-up visit	All assessments	+ 7 days
150-day Safety Follow- up visit	All assessments	+ 14 days
Survival follow-up	All assessments	± 14 days

Table 8-2 Assessment Schedule, Part 1 (for all arms with 28-day cycles)

Period	Screening											Core Treatment ¹											
Cycle				C	ycle	1				С	ycle	2			Cycle 3				C	ycle	4	Су	cle 5
Days	-28 to -1	1	2	5	6	8	15	16	1	2	5	6	15	1	2	5	8	15	1	2	5	1	2 5
Informed consent	Х																						
IRT screening call	X																						
Inclusion/exclusion criteria	Х																						
IRT eligibility checklist and allocation call		Х																					
Demography	Х																						
Medical history	X																			\prod			
Disease diagnosis	Х																						
Prior ruxolitinib therapy	Х																						
Prior anti-neoplastic therapy	X																			\prod			
Prior/concomitant medications	Х												Х (а	t eve	ery clinic visit)								
Non-drug therapies and procedures	X											,	Х (а	t eve	ery clinic visit)								
Transfusion record (PRBC and platelets)	X											,	Х (а	t eve	ery clinic visit)								
Physical examination	S	S							S					S					S			S	
ECOG performance status	Х	Х							Х					Х					Х			Χ	
Height	Х																			\prod			
Weight	Х	Х					X ²		Х					Х					Х	\prod		Χ	
Vital signs	Х												Х (а	t ev	ery clinic visit)								
Spleen length measurement by palpation	Х	Х					Х		Х				Х	Х				Χ	Х	\prod		Χ	
Laboratory assessments														-									
Hematology	Х	Х					Х		Х				Х	Х				Х	Х			Χ	
Chemistry	Х	Х							Х					Х					Х			Χ	
Additional chemistry for siremadlin safety monitoring ³			Х	Х	Х					Х	Х	Х			Х	Х				Х	X		хх

Confidential

Page 142 of 267 Protocol No. CINC424H12201

Period	Screening	ning Core Treatment ¹																					
Cycle				Су	cle	1				(Cycle	2				Cycle 3			С	ycle	e 4	Су	/cle 5
Days	-28 to -1	1	2	5	6	8	15 1	16	1	2	5			15	1		1	3 15	1	2	5	1	2 5
Coagulation	X												Х (as (clinic	cally indicated)							
Urinalysis	X												Χ (as	clini	cally indicated)							
Thyroid function	X												Χ (as	clini	cally indicated)							
Pregnancy test - serum	S																						
Pregnancy test - urine or serum		S							S						S				S			S	
Hepatitis test	X ⁵												Χ (as	clini	cally indicated)							
HIV screen	S ⁴																Ī						
Serology exam		X ⁶											Χ	(as	clin	ically indicated)							

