Period		Co	re '	Treatment ¹	End of Treatment (Core) ²²	Extensio	n Treatment	End of Treatment (Extension)		Safety Follow-up ¹²				
Cycle	C	/cle	6	Cycle 7 and subsequent cycles*		Cycle 1 ²²	Cycle 2 and subsequent cycles							
Dovo	1	2	5	1		4	1		30 Days	90 & 150 Days	105 Days			
Days	ı		5	ı		ı	ı		(All)	(sabatolimab)	(Crizanlizumab)			
Informed consent						X								
IRT screening call														
Inclusion/exclusion criteria						Х								
IRT eligibility checklist and allocation call						Х								
Demography														
Medical history														
Disease diagnosis														
Prior ruxolitinib therapy														
Prior anti-neoplastic therapy														
Prior/concomitant medications	Х	(at	eve	ery clinic visit)	Х	Х	Х	Х	Х	х	Х			

Period		Co	ore '	Treatment ¹	End of Treatment (Core) ²²	Extension	n Treatment	End of Treatment (Extension)		Safety Follow	-up ¹²
Cycle	Cy	ycle	6	Cycle 7 and subsequent cycles*		Cycle 1 ²²	Cycle 2 and subsequent cycles				
Days	1	2	5	1		1	1		30 Days (All)	90 & 150 Days (sabatolimab)	105 Days (Crizanlizumab)
Non-drug therapies and procedures	Х	(at	eve	ery clinic visit)	Х	х	Х	Х	Х	Х	X
Transfusion record (PRBC and platelets)	Х	(at	eve	ery clinic visit)	Х	X ²²	Х	Х	Х	x	X
Physical examination	S			S	S	S	S	S	S	S	S
ECOG performance status	Х			X	Χ	X ²²	X	Х			
Height											
Weight	Х			Х	Х	X ²²	Х	Х			
Vital signs	Х	(at	eve	ery clinic visit)	Х	X ²²	X (at every clinic visit)	Х	Х	х	х
Spleen length measurement by palpation	Х			х	Х	X ²²	Х	Х			
Laboratory assessments							-				
Hematology	Х			X	Х	X ²²	Х	Х	Х	X	Х
Chemistry	Х			Х	Х	X ²²	Х	Х	Х	Х	Х
Additional chemistry for siremadlin safety monitoring ³		х	х								
Coagulation	X (as	clini	ically indicated)		X (as clinically indicated)					
Urinalysis	Χ (as	clini	ically indicated)	Х	X ²²		Х			
Thyroid function	Χ (as	clini	ically indicated)	Х	X ²²		Х			
Pregnancy test - serum					S			S	S	S	S

Period		Co	ore '	Treatment ¹	End of Treatment (Core) ²²	Extension	n Treatment	End of Treatment (Extension)		Safety Follow	-up ¹²
Cycle	C	ycle	6	Cycle 7 and subsequent cycles*		Cycle 1 ²²	Cycle 2 and subsequent cycles				
Days	1	2	5	1		1	1		30 Days (All)	90 & 150 Days (sabatolimab)	105 Days (Crizanlizumab)
Pregnancy test - urine or serum	s			S		S	S		,		,
Hepatitis test				clinically cated)	X		X (as clinically indicated)	Х			
HIV screen											
Serology exam				clinically cated)		X (as clinically indicated)	X (as clinically indicated)				

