Subjects who discontinue study treatment or who decide they do not wish to participate in the study further should NOT be considered withdrawn from the study UNLESS they withdraw their consent (see 'Withdrawal of Informed Consent' section). Where possible, all subjects should return for and End of Treatment (EOT) visit within 7 days after discontinuation of permanent study treatment (all investigational drugs), at which time all of the assessments for EOT indicated in Table 8-2, Table 8-3, Table 8-4, or Table 8-5 should be performed, including a physical examination, vital signs, height, weight, ECOG performance status, ECG, concomitant medications, non-drug therapy and procedures, collection of AEs and any transfusions, laboratory assessments, spleen palpation (CT or MRI imaging, blood sampling for PK/PD , bone marrow biopsy or aspirate, and, if applicable, immunogenicity for crizanlizumab, sabatolimab or NIS793. If they fail to return for these assessments for unknown reasons, every effort (e.g. telephone, e-mail, letter) should be made to contact the subject/predesignated contact as specified in the lost to follow-up Section 9.1.3. This contact should preferably be done according to the study visit schedule.

If the subject cannot or is unwilling to attend any visit(s), the site staff should maintain regular telephone contact with the subject, or with a person pre-designated by the subject. This telephone contact should preferably be done according to the study visit schedule.

After study treatment discontinuation, all subjects must have a Safety Follow-up visit 30 days after permanent study treatment discontinuation as described in Section 9.2.

The investigator must also contact the IRT to register the subject's discontinuation from study treatment.

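### In the 28-day arms the SAP summarises coagulation, urinalysis and thyroid function by cycle, although no on-treatment cycle visit schedules them, so the post-baseline rows come from a selected subset

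*SAP*

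**What the plan says.** SAP 2.1.1 explains the purpose of its windows: "In order to summarize data collected over time (including unscheduled visits), the assessments will be time slotted". Table 2-2, headed "Time windows for ePROs, laboratory assessments (chemistry, coagulation, urinalysis and thyroid function" (the rest of the heading is redacted), gives one window per cycle from Cycle 2 Day 1 onward. Its footnote adds that "EOT core and EOT extension assessments are mapped to the corresponding time points based on the defined time window". SAP 2.8.3 then states for laboratory data in general: "Summary statistics will be provided by treatment and visit/time". It makes no exception for tests without a per-cycle schedule. Protocol 12.5.2 plans the same by-visit statistics for the core phase.

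Protocol Table 8-2, for the 28-day arms, marks all three tests at screening. For the core cycles the entry for each is "X (as clinically indicated". At EOT core and EOT extension, urinalysis and thyroid function carry a plain mark and coagulation carries none. Protocol 9.1.1 makes the EOT tests routine for those who leave treatment: subjects return for a visit "at which time all of the assessments for EOT indicated in Table 8-2, Table 8-3, Table 8-4, or Table 8-5 should be performed".

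**The concern.** Table 2-2 treats these three tests like chemistry, which Table 8-2 schedules on Day 1 of every cycle. The baseline row describes essentially every treated subject. A later row describes whoever happened to be tested, so a change from baseline across rows mixes any treatment effect with the reason for testing. The affected continuous measures are INR and APTT for coagulation, and TSH and free T4 for thyroid function (Protocol Table 8-11).

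Laboratory abnormalities belong to the secondary safety endpoint, and Protocol 4.5 names immune-related events as an anticipated risk with sabatolimab and NIS793. A reader of the study report could therefore look to these rows for a trend over time that they cannot show.

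**Working it through.** No sample-size or error-rate figure is at issue. The check sets the schedule beside the windows.

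**1. Do the windows catch every indicated test?** Table 2-2 gives days 15–42, 43–70, 71–98, 99–126 and 127–154 for Cycles 2 to 6. After that, Cycle 6+k runs from (6+k−1)×28+1−14 to (6+k−1)×28+14:
- k=1: 6×28+1−14 = 155 to 6×28+14 = 182
- k=2: 7×28+1−14 = 183 to 7×28+14 = 210

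The windows have no gaps. Every on-treatment value from day 15 onward, whether indicated or from an EOT visit, falls in some cycle's window.

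**2. What is scheduled after screening?** Counts per subject, 28-day arms, from Table 8-2:

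| Test | Core cycles | EOT core | EOT extension (if entered) |
|---|---|---|---|
| Chemistry | Day 1 of every cycle | 1 | 1 |
| Coagulation | 0 (as indicated) | 0 | 0 |
| Urinalysis | 0 (as indicated) | 1 | 1 |
| Thyroid function | 0 (as indicated) | 1 | 1 |

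Footnote 22 of Table 8-2 makes the EOT core sample serve also as extension Cycle 1 Day 1, so it is one sample, not two. From extension Cycle 2 the table schedules none of the three tests until EOT extension.

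**3. What does a post-baseline row contain?**
- Coagulation: indicated tests only.
- Urinalysis and thyroid function: indicated tests, plus routine EOT samples placed in whichever cycle the subject's treatment phase ended.

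Neither group represents the subjects on treatment at that cycle. The EOT samples come from subjects who stopped or completed core treatment, or who moved to the extension (at most 4 subjects, SAP 1.1). Reasons for stopping in Protocol 9.1.1 include adverse events, progression and lack of benefit.

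**4. The NIS793 arm.** Table 8-4 schedules urinalysis on Day 1 of every 21-day cycle, so by-visit urinalysis is meaningful there. In that arm coagulation remains as indicated, and thyroid function is as indicated until EOT. A urinalysis row thus has scheduled coverage in one arm and selected coverage in the others.

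**The case against.** **No such tables may be intended.** The itemised outputs in SAP 2.8.3 are introduced for hematology and biochemistry, and the shift tables use the worst on-treatment value, not values per visit. Urinalysis is mainly a dipstick panel, for which a mean has little sense. This has some force. But the by-visit sentence precedes that list and covers laboratory data generally, and Table 2-2 names the three tests. If no by-visit summary is meant, Table 2-2 should not list them, so an edit is needed either way.

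**A reader might infer that the later rows show only suspected cases.** The documents do not support that. Urinalysis and thyroid function also have routine EOT samples. Clinical indication is also broader than a suspected abnormal result: Protocol 6.2.1 asks for coagulation monitoring when anticoagulant or antiplatelet drugs are started.

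**A reader might also infer that the tables will show a false deterioration of some calculable size.** That is not supported either. The documents give no testing probabilities. The general convention in SAP 2.1 takes percentages over the relevant population or subgroup, with a missing category as applicable, so a tested-only denominator is not clearly prescribed. Counting untested subjects in the denominator could understate abnormality instead.

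**The consequence is limited.** This stands. Part 1 is descriptive and non-randomised, with about 6 subjects per run-in arm or siremadlin dose cohort. All assessments are already to be listed. The recommended dose rests on dose-limiting toxicities and the wider safety, PK and PD data, not on these rows. But with so few subjects, one or two indicated tests could make up a whole row.

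**Conclusion.** The point holds as a minor one. In the 28-day arms the SAP plans per-cycle summaries for three tests that have no per-cycle schedule. The mismatch is complete for coagulation: no scheduled test after screening. For urinalysis and thyroid function it is partial: one scheduled sample at EOT core and, for those who enter the extension, one more at EOT extension. The post-baseline rows are selected and cannot be interpreted as visit means or as changes from an all-subject baseline. The direction and size of any bias cannot be determined from the documents. The baseline row is unaffected.

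This rests on reading the general by-visit sentence in SAP 2.8.3 together with the explicit naming of the tests in Table 2-2.

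**What to change.** In SAP Table 2-2 and 2.8.3:
- Remove coagulation and thyroid function (all arms) and urinalysis (28-day arms) from the by-visit windows and summaries.
- Keep the listings already planned, and use the visit label (screening, EOT, other) to show which values were scheduled. No new data field is needed.
- Summarise thyroid function and urinalysis as baseline to EOT, with the number tested.
- Show the number tested in any worst-on-treatment summary of these tests.
- Keep by-visit urinalysis for the NIS793 arm only, with 21-day windows. In Table 2-2, Cycle 4 Day 1 of that arm (3×21+1 = day 64) falls in the window labelled Cycle 3 (days 43–70).

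The cost is SAP wording and fewer tables. The one downside is that sparse indicated values then appear only in listings, apart from any that enter a worst-on-treatment summary.
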